## 7.1 Treatments Administered

Treatments should be administered according to [Table 7.1-1](#).

Dosing calculations should be based on the body weight assessed at baseline. It is not necessary to recalculate subsequent doses if the participant weight is within 10% of the weight used to calculate the previous dose. All doses should be rounded up or to the nearest milligram per institutional standard.

When study treatments (nivolumab and ipilimumab) are to be administered on the same day, nivolumab is to be administered first. Nivolumab infusion must be promptly followed by a flush of diluent to clear the line of nivolumab before starting the ipilimumab infusion. The second infusion will always be the ipilimumab study treatment and will start after the infusion line has been flushed, the filters have been changed, and the participant has been observed to ensure no infusion reaction has occurred.

There will be no dose increases or reductions of nivolumab allowed. Participants may be dosed no less than 19 days from the previous dose during Q3W cycles. For Q4W dosing cycles, participants may be dosed within a  $\pm$  3-day window. Premedications are not recommended for the first dose of nivolumab.

Participants should be carefully monitored for infusion reactions during nivolumab administration. If an acute infusion reaction is noted, participants should be managed according to [Section 7.4.5](#).

Doses of nivolumab may be interrupted, delayed, or discontinued depending on how well the participant tolerates the treatment. Dosing visits are not skipped, only delayed.

Treatment should be continued until disease progression or unacceptable toxicity, with a maximum nivolumab treatment of 24 months from the first dose in Cycle 1.

Nivolumab injection, 100 mg/10 mL (10 mg/mL) is to be administered as a 30-minute IV infusion through a 0.2- $\mu$ m to 1.2- $\mu$ m pore size, low-protein binding in-line filter at the protocol-specified doses. It is not to be administered as an IV push or bolus injection. For instructions on storage, preparation, and administration of nivolumab, please refer to the current IB and/or pharmacy manual. Care must be taken to ensure sterility of the prepared solution, as the product does not contain any antimicrobial preservative or bacteriostatic agent.

For instructions on storage, preparation, and administration of ipilimumab, please refer to the current IB and/or pharmacy manual.

Ipilimumab is to be administered as a 30-minute IV infusion and may be infused using a volumetric pump with a 0.2- $\mu$ m to 1.2- $\mu$ m low-protein binding in-line filter at the protocol-specified dose. It is not to be administered as an IV push or bolus injections. Care must be taken to ensure sterility of the prepared solutions, as the drug product does not contain any antimicrobial preservatives or bacteriostatic agents. At the end of the infusion, flush the line with a sufficient quantity of diluent.

**Table 7.1-1: Selection and Timing of Dose**

Study Treatment	Dosage level(s) and Formulation	Frequency of Administration	Route of Administration
Nivolumab	3 mg/kg 480 mg	Q3W for 4 doses Q4W (maintenance)	IV
Ipilimumab	1 mg/kg	Q3W for 4 doses	IV

Abbreviations: IV = intravenous; Q3W = every 3 weeks; Q4W = every 4 weeks

Note: After 4 doses of study treatment Q3W, participants receive nivolumab monotherapy. Monotherapy begins 3 weeks after their last Q3W dose.

## 7.2 Method of Treatment Assignment

Not applicable.

## 7.3 Blinding

This is a non-randomized, open-label study; blinding procedures are not applicable.

## 7.4 Dosage Modification

I-O agents are associated with AEs that can differ in type, severity, and duration than AEs caused by other therapeutic classes. Nivolumab and ipilimumab are considered I-O agents in this protocol. Early recognition and management of AEs associated with I-O agents may mitigate severe toxicity. The safety profile of nivolumab and in combination of ipilimumab is described in the IB. Management of drug-related AE includes dose modification and medical interventions, and supportive care should be carefully considered. The recommended management algorithms for IMAE are outlined in [Appendix 5](#) in the following groups: GI, Renal, Pulmonary, Hepatic, Endocrinopathy, Skin, and Neurological. In general, both nivolumab and ipilimumab have similar safety profiles and overlapping IMAEs. The management algorithms and criteria for dose delay, resumption, or discontinuation should be applicable for both drugs. Both drugs should be delayed, resumed, or discontinued when the criteria are met.

### 7.4.1 Dose Modifications

Dose reductions or dose increases of nivolumab or ipilimumab are not permitted.

### 7.4.2 Dose Delay Criteria

Nivolumab and ipilimumab administration should be delayed for the following:

- Grade 2 nonskin, drug-related AE, with the exception of fatigue
- Grade 2 drug-related creatinine, AST, ALT, and/or TBili abnormalities
- Grade 3 skin, drug-related AE
- Grade 3 drug-related laboratory abnormality, with the following exceptions:
  - Grade 3 lymphopenia or asymptomatic amylase or lipase does not require dose delay.
  - Grade  $\geq 3$  AST, ALT, and/or TBili will require dose discontinuation (see [Section 7.4.4](#)).
- Any AE, laboratory abnormality, or intercurrent illness that, in the judgment of the investigator, warrants delaying the dose of study medication

During Cycles 1 to 4, both nivolumab and ipilimumab must be delayed at the same time.

Participants who require delay of study treatment should be re-evaluated weekly or more frequently if clinically indicated and resume study treatment dosing when retreatment criteria are met. Tumor and other assessments should continue as per protocol even if dosing is delayed.

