## 6.2 Exclusion Criteria

### 1) Medical Conditions

- a) Any active central nervous system (CNS) metastases
- b) Any prior AE that meets the criteria for treatment discontinuation as described in [Section 7.4.4](#), with the exception of patients with prior history of adrenal insufficiency that are under control with hormone replacement.
- c) Participants with treated CNS metastases for at least 1 month are eligible as long as they meet the following criteria:
  - i) Treated CNS metastases are defined as having no ongoing requirement for corticosteroids for at least 2 weeks (14 days) prior to first dose and no evidence of progression after treatment completed prior to first dose, as ascertained by clinical examination and brain imaging (magnetic resonance imaging [MRI] or CT). Stable dose of anticonvulsants is allowed. Treatment for CNS metastases may include whole brain radiotherapy, radiosurgery (eg, radiosurgery, gamma knife, linear accelerator, or equivalent) or a combination as deemed appropriate by the treating physician.
  - d) Participants with an active, known or suspected autoimmune disease. Participants with type I diabetes mellitus, hypothyroidism only requiring hormone replacement, skin disorders (such as vitiligo, psoriasis, or alopecia) not requiring systemic treatment, or conditions not expected to recur in the absence of an external trigger (eg, celiac disease) are permitted to enroll.
  - e) Participants with a condition requiring systemic treatment with either corticosteroids (> 10 mg daily prednisone equivalent) or other immunosuppressive medications within 14 days of first dose. Inhaled or topical steroids and adrenal replacement steroid doses > 10 mg daily prednisone equivalent are permitted in the absence of active autoimmune disease.
  - f) Uncontrolled adrenal insufficiency
  - g) Active infection requiring systemic therapy within 14 days prior to the first treatment dose
  - h) Not applicable per revised protocol 01.

- i) Participants with HIV infections are excluded if any of the following applies:
  - i) CD4+ T-cell count < 350 cells/ $\mu$ L
  - ii) Any AIDS-defining opportunistic infection occurred in the last 12 months
  - iii) HIV viral load is  $\geq$  400 copies/mL
  - iv) Antiretroviral therapy has been administered at current doses for less than 4 weeks
  - v) The participant is not on antiretroviral therapy
- j) Participants with a history of chronic hepatitis B or C are excluded if any of the following applies:

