#### **7.4.3 Criteria to Resume Treatment**

Delayed doses of study treatment should be administered as soon as the participant meets criteria to resume treatment. If a dose has been delayed, the participant should not wait until the next scheduled dosing date.

Participants may resume study treatment when the drug-related AEs resolve to Grade  $\leq 1$  or baseline value, with the following exceptions:

- Participants may resume treatment in the presence of Grade 2 fatigue.
- Participants who have not experienced a Grade 3 drug-related skin AE may resume treatment in the presence of Grade 2 skin toxicity.
- For participants with Grade 2 AST, ALT, and/or TBili abnormalities, dosing may resume when laboratory values return to baseline and management with corticosteroids, if needed, has been completed.
- Drug-related pulmonary toxicity, diarrhea, or colitis must have resolved to baseline before treatment is resumed. Participants with persistent Grade 1 pneumonitis after completion of a steroid taper over at least 1 month may be eligible for retreatment if discussed with and approved by the BMS medical monitor or designee.
- Participants with drug-related endocrinopathies that are adequately controlled with only physiologic hormone replacement may resume treatment.

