#### **7.4.4.1 Nivolumab Dose Discontinuation**

Nivolumab treatment should be permanently discontinued for the following:

- Any Grade 2 drug-related uveitis, eye pain or blurred vision that does not respond to topical therapy and does not improve to Grade 1 severity within the retreatment period OR requires systemic treatment
- Any Grade 3 non-skin, drug-related AE lasting  $> 7$  days or recurs, with the following exceptions for laboratory abnormalities, neurologic toxicity, drug-related uveitis, pneumonitis, bronchospasm, hypersensitivity reactions, infusion reactions, and endocrinopathies:
  - Grade 3 drug-related neurologic toxicity, uveitis, pneumonitis, bronchospasm, myocarditis, hypersensitivity reaction, or infusion reaction of any duration requires discontinuation
  - Grade 3 drug-related endocrinopathies, adequately controlled with only physiologic hormone replacement do not require discontinuation. Adrenal insufficiency requires discontinuation regardless of control with hormone replacement.
  - Grade 3 drug-related laboratory abnormalities do not require treatment discontinuation except:
    - ◆ Grade 3 drug-related thrombocytopenia  $> 7$  days or associated with bleeding requires discontinuation
    - ◆ Grade  $\geq 3$  drug-related AST, ALT, or TBili requires discontinuation\*
    - ◆ Concurrent AST or ALT  $> 3 \times$  ULN and TBili  $> 2 \times$  ULN
- \*In most cases of Grade 3 AST or ALT elevation, study treatment will be permanently discontinued. If the investigator determines a possible favorable benefit/risk ratio that warrants continuation of study treatment, a discussion between the investigator and the BMS medical monitor/designee must occur.
- Any Grade 4 drug-related AE or laboratory abnormality (including but not limited to creatinine, AST, ALT, or TBili), except for the following events, which do not require discontinuation:
  - Grade 4 neutropenia  $\leq 7$  days
  - Grade 4 lymphopenia or leukopenia or asymptomatic amylase or lipase
  - Isolated Grade 4 electrolyte imbalances/abnormalities that are not associated with clinical sequelae and are corrected with supplementation/appropriate management within 72 hours of their onset

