#### **7.4.4.2 *Ipilimumab Dose Discontinuation***

Ipilimumab treatment should be permanently discontinued for the following:

- Any Grade 2 drug-related uveitis, eye pain, or blurred vision that does not respond to topical therapy and does not improve to Grade 1 severity within the retreatment period OR requires systemic treatment
- Any Grade 3 non-skin, drug-related AE lasting > 7 days, or recurs, with the following exceptions for laboratory abnormalities, diarrhea, colitis, neurologic toxicity, drug-related uveitis, pneumonitis, bronchospasm, hypersensitivity reactions, infusion reactions, and endocrinopathies:
  - Grade 3 drug-related diarrhea, colitis, neurologic toxicity, uveitis, pneumonitis, bronchospasm, myocarditis, hypersensitivity reaction, or infusion reaction of any duration requires discontinuation.
  - Grade 3 drug-related endocrinopathies adequately controlled with only physiologic hormone replacement do not require discontinuation. Adrenal insufficiency requires discontinuation regardless of control with hormone replacement.
  - Grade 3 drug-related laboratory abnormalities do not require treatment discontinuation except:
    - ◆ Grade 3 drug-related thrombocytopenia > 7 days or associated with bleeding requires discontinuation
    - ◆ Any drug-related liver function test abnormality that meets the following criteria require discontinuation:
      - Grade  $\geq$  3 drug-related AST, ALT, or TBili requires discontinuation\*
      - Concurrent AST or ALT > 3 $\times$  ULN and TBili > 2 $\times$  ULN

\*In most cases of Grade 3 AST or ALT elevation, study treatment will be permanently discontinued. If the investigator determines a possible favorable benefit/risk ratio that warrants continuation of study treatment, a discussion between the investigator and the BMS medical monitor/designee must occur.

- Any Grade 4 drug-related AE or laboratory abnormality (including but not limited to creatinine, AST, ALT, and TBili), except for the following events, which do not require discontinuation:
  - Grade 4 neutropenia  $\leq$  7 days
  - Grade 4 lymphopenia or leukopenia or asymptomatic amylase or lipase

- Isolated Grade 4 electrolyte imbalances/abnormalities that are not associated with clinical sequelae and are corrected with supplementation/appropriate management within 72 hours of their onset

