## **8 DISCONTINUATION CRITERIA**

### **8.1 Discontinuation From Study Treatment**

The assessment for discontinuation of nivolumab should be made separately from the assessment made for discontinuation of ipilimumab. Although there is overlap among the discontinuation criteria, if discontinuation criteria are met for ipilimumab but not for nivolumab, treatment with nivolumab may continue if ipilimumab is discontinued.

If a participant meets the criteria for discontinuation and the investigator is unable to determine whether the event is related to both or 1 study drug, the participant should discontinue both nivolumab and ipilimumab and be taken off the treatment phase of the study.

Participants MUST discontinue IP (and non-IP at the discretion of the investigator) for any of the following reasons:

- Participant's request to stop study treatment. Participants who request to discontinue study treatment will remain in the study and must continue to be followed for protocol-specified follow-up procedures. The only exception to this is when a participant specifically withdraws consent for any further contact with him/her or persons previously authorized by participant to provide this information.
- Any clinical AE, laboratory abnormality, or intercurrent illness that, in the opinion of the investigator, indicates that continued participation in the study is not in the best interest of the participant
- Termination of the study by BMS
- Loss of ability to freely provide consent through imprisonment or involuntarily incarceration for treatment of either a psychiatric or physical (eg, infectious disease) illness. (Note: Under specific circumstances, a participant who has been imprisoned may be permitted to continue as a participant. Strict conditions apply, and BMS approval is required.)
- Criteria listed in [Section 7.4.4](#).
- Disease progression of RCC or occurrence of a secondary malignancy that requires systemic therapy for treatment

Refer to the Schedule of Activities (Section 2) for data to be collected at the time of treatment discontinuation and follow-up and for any further evaluations that can be completed

In the case of pregnancy, the investigator must immediately, within 24 hours of awareness of the pregnancy, notify the BMS medical monitor/designee of this event. In most cases, the study treatment will be permanently discontinued in an appropriate manner (eg, dose tapering, if necessary, for participant safety). Refer to [Section 9.2.5](#).

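### The liver delay and restart rules make no exception for the concurrent AST/ALT and bilirubin rise that Section 7.4.4 lists as a permanent stop, and the placing of that stop leaves it unclear whether it applies below Grade 3

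*Combined protocol and SAP*

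**What the plan says.** Five places in the protocol bear on this.

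- **Section 7.4.2 (delay).** Both drugs are delayed for "Grade 2 drug-related creatinine, AST, ALT, and/or TBili abnormalities". The only liver pointer to Section 7.4.4 is for Grade 3 or higher: "AST, ALT, and/or TBili will require dose discontinuation (see".
- **Section 7.4.3 (restart).** "For participants with Grade 2 AST, ALT, and/or TBili abnormalities, dosing may resume when laboratory values return to baseline", provided any corticosteroid course is complete. The section also asks for a delayed dose to be given promptly once the restart criteria are met.
- **Section 7.4.4.1 (nivolumab stop).** Under the parent bullet "Grade 3 drug-related laboratory abnormalities do not require treatment discontinuation except" come three exceptions: thrombocytopenia, Grade 3 or higher AST, ALT or bilirubin, and a line beginning "Concurrent AST or ALT" that combines AST or ALT > 3 × ULN with bilirubin > 2 × ULN.
- **Section 7.4.4.2 (ipilimumab stop).** The same limits sit under the same Grade 3 parent bullet, but with an extra lead-in: "Any drug-related liver function test abnormality that meets the following criteria require discontinuation".
- **Section 8.1.** "Participants MUST discontinue IP (and non-IP at the discretion of the investigator) for any of the following reasons"; the criteria of Section 7.4.4 are among those reasons.

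Exclusion 1) b) in Section 6.2 reuses the stop list for eligibility: "Any prior AE that meets the criteria for treatment discontinuation as described in" Section 7.4.4, apart from controlled adrenal insufficiency.

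**The concern.** The words and/or in Sections 7.4.2 and 7.4.3 take in AST/ALT and bilirubin raised together. A site that sees both values at Grade 2 finds a delay rule and a restart rule that fit exactly, and no sign in either that some of these combinations may belong to the permanent-stop list. If it then looks at the stop list, it finds the relevant line indented under a Grade 3 heading and may conclude that the line does not apply.

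At stake is whether a participant with a concurrent rise is dosed again. The protocol itself gives this pattern weight: Section 9.2.7 uses the same two limits, with further conditions on cholestasis and other causes, to define potential drug-induced liver injury, reportable as an SAE. Because exclusion 1) b) refers to Section 7.4.4, the same uncertainty about the line's reach carries into eligibility for candidates who had such a rise on their first course.

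**Working it through.** There is no planned figure to reproduce. The check is a comparison of the rules, plus one overlap condition.

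**Step 1. Can two Grade 2 values meet the concurrent line?** Let Grade 2 reach up to a × ULN for AST/ALT and b × ULN for bilirubin. The protocol names CTCAE version 5.0 but does not print a or b, so both are assumptions. Two Grade 2 values can meet the line only if a > 3 and b > 2. All 25 pairs from a = 2.5, 3, 4, 5, 6 and b = 1.5, 2, 2.5, 3, 4 were tried:

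| | b = 1.5 or 2 | b = 2.5, 3 or 4 |
|---|---|---|
| a = 2.5 or 3 | no overlap | no overlap |
| a = 4, 5 or 6 | no overlap | overlap |

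Nine pairs (3 × 3) overlap and 16 do not. With a = 5 and b = 3, for example, the overlap is AST/ALT above 3 and up to 5 × ULN with bilirubin above 2 and up to 3 × ULN.

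**Step 2. Does the text point to an overlap?** Partly. Grade 3 or higher AST, ALT or bilirubin is already a listed stop, so a separate concurrent line adds little unless it reaches lower grades. It has one other possible role: the Grade 3 line carries a footnote allowing discussion of continued treatment after a Grade 3 AST or ALT rise, and the concurrent line carries no footnote. It could therefore serve to remove that discretion when bilirubin is also raised.

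**Step 3. What happens to two overlapping Grade 2 values?**

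| Reading of the concurrent line | Nivolumab | Ipilimumab |
|---|---|---|
| Limited to Grade 3 by its parent bullet, both drugs | delay, restart permitted | delay, restart permitted |
| Limited for nivolumab; the ipilimumab lead-in extends it to any liver abnormality | delay, restart permitted | stop |
| Stands alone, both drugs | stop | stop |

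The middle row is possible because Section 7.4.4 assesses the drugs separately and lets nivolumab continue when only the ipilimumab criteria are met, unless the investigator cannot tell which drug is responsible. Section 7.4, by contrast, says the delay, restart and stop criteria should apply to both drugs.

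**Step 4. How many participants?** Table 3.2.6.4-2 gives drug-related hepatic events in CA209214 as 101 of 547, of which 45 were Grade 3-4. That leaves 101 − 45 = 56, and 56/547 = 10.2%, with Grade 1 or 2 events. Carried over to 96 participants this would be 0.102 × 96 = 9.8. It is context, not an estimate: it includes Grade 1 events, comes from first-line patients, and does not show how many had both values raised. Any share of it would be an assumption.

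**The case against.** The strongest reply is that Section 8.1 settles the matter. It makes the Section 7.4.4 criteria compulsory, while Section 7.4.3 only permits restart, and a permission does not cancel an obligation. Other stops, such as certain Grade 2 uveitis or Grade 3 thrombocytopenia with bleeding, also override the delay list without a cross-reference. This stands as far as it goes: where the criterion is met, the stop governs. But the obligation takes effect only once the criterion is met, and the Grade 3 nesting leaves exactly that open for two lower-grade values.

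Some stronger readings are tempting, and the documents do not support them.

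- *Two opposite instructions of equal force.* They are not equal, because of Section 8.1.
- *The concurrent line is empty at Grade 3.* It may limit the footnoted discretion (Step 2).
- *Participants who enter above one limit meet the line as soon as the other value rises.* Section 6.2 does admit AST/ALT up to 5 × ULN with liver metastases, and bilirubin below 3 × ULN with Gilbert syndrome. But the parent bullets concern drug-related abnormalities, which an elevation already present at entry is not plainly.
- *Exclusion 1) b) conflicts with the restart rule.* It refers only to Section 7.4.4; what it inherits is the nesting question.
- *DCR is distorted.* Nothing quantifies this, and tumor assessments continue after treatment stops (Sections 7.4.4 and 9.1.1.2).

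The hepatic algorithm in Appendix 5 is a figure that could not be read for this review. If it addresses the combined pattern, it belongs in the reconciliation.

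**Conclusion.** The point holds as a wording defect with a bearing on participant safety. The delay and restart sections omit an exception or cross-reference for the concurrent rise, and the stop line is placed so that its reach below Grade 3 is unclear, more so for nivolumab than for ipilimumab. The stop is probably what governs, but a site that follows the liver restart rule literally could re-dose a pattern that Section 7.4.4 lists as a permanent stop.

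This rests on one assumption: that Grade 2 extends above 3 × ULN for AST/ALT and above 2 × ULN for bilirubin. If either fails, two Grade 2 values cannot meet the line and the overlap disappears. The number of participants affected cannot be derived from the documents and is probably small. There is no effect on sample size, power or type I error.

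**What to change.** Reconcile Sections 7.4.2, 7.4.3, 7.4.4.1, 7.4.4.2 and 8.1 so that the concurrent elevation has one stated action:

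1. Either place the concurrent line outside the Grade 3 sub-list, or state that it is limited to Grade 3.
2. Use the same wording and nesting for nivolumab and ipilimumab, or say that a difference is intended.
3. Cross-reference the line in Sections 7.4.2 and 7.4.3, so that the and/or wording is expressly with or without the concurrent rise.

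Exclusion 1) b) then follows through its reference to Section 7.4.4 and needs no separate edit. Which action applies is for the sponsor to decide on clinical grounds.

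The cost is a few sentences in the next amendment, with no added tests, visits or participants.
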